#### 6. STUDY INTERVENTION

#### 6.1. Identity of Test Articles

The following contact lenses will be used in this study:

Table 1: Test Articles

	Control	Test
Name	1-DAY ACUVUE ® DEFINE ® Vivid style	Etafilcon A with PVP with cosmetic pattern-Green*
Manufacturer	Johnson & Johnson	Johnson & Johnson
Lens Material	Etafilcon A	Etafilcon A
Nominal Base Curve @ 22°C	8.5 mm	8.5 mm
Nominal Diameter @ 22°C	14.2 mm	14.2 mm
Nominal Distance Powers (D)	-1.00 to -6.00 D	-1.00 to -6.00 D
Modality in Current Study	Daily	Daily
Replacement Frequency	Daily	Daily

Packaging Form (vial,	Blister	Blister
blister, etc.)		

\*The green variant was selected to be used in the study because it contains the highest pigment load of the current project variants.

Each subject will wear approximately 2 of each lens type.

#### 6.2. Ancillary Supplies/Products

The following solutions will be used in this study:

Sensitive Eyes Plus (Bausch & Lomb) or country-specific alternative approved by the sponsor, FluStrips (Contacare) or country-specific alternative approved by the sponsor, and Tears Naturale Free (Alcon) or country-specific alternative approved by the sponsor.

Table 2: Ancillary Supplies

		Solution	
Solution Name/Description	Sensitive Eyes plus Saline (or other sponsor-approved product)	Tears Naturale Free (or other sponsor-approved product)	FluStrips Fluorescein (or other sponsor- approved product)
Manufacturer	Bausch & Lomb	Alcon	Contacare Ophthalmics Diagnostics (EOU)
Preservative	None	None	None
Other distinguishing items (dye, packaging, approval status, etc.	NA	NA	D&C Yellow No. 8, 0.6 mg

[figure not shown]
#### 6.3. Administration of Test Articles

Test articles will be dispensed to subjects meeting all eligibility requirements, including any dispensing requirements set forth in this clinical protocol. Subjects will be dispensed an adequate supply of test articles to complete the study. Lost or damaged test articles may be replaced at the discretion of the Investigator and/or the Sponsor.

#### 6.4. Packaging and Labeling

The test articles will be over-labeled to mask the subject/Investigators to the identity of the lens. The labels will meet the country-specific labeling guidelines for clinical studies involving investigational contact lenses. The test articles will be in plastic bags as the secondary packaging form.

The sample study label is shown below: CPL-Label- A

#### 6.5. Storage Conditions

Test articles will be maintained at ambient temperatures at the clinical site. Test articles must be kept under secure conditions.

#### 6.6. Collection and Storage of Samples

No samples will be collected as part of the study procedures.

When possible, any lens or test article associated with an Adverse Events and/or a Product Quality Complaint must be retained and stored in a glass vial with moderate solution pending directions from the sponsor for potential return back to JJVC.

#### 6.7. Accountability of Test Articles

JJVC will provide the Investigator with sufficient quantities of study articles and supplies to complete the investigation. The Investigator is asked to retain all lens shipment documentation for the test article accountability records.

Test articles must be kept in a locked storage cabinet, accessible only to those assigned by the Investigator for dispensing. The Investigator may delegate this activity to authorized study site personnel listed on the Site Delegation Log. All test articles must be accounted. This includes:

- 1. What was dispensed for the subject for trial fitting, to wear out of the office, or issued for the subject to replace appropriately between visits.
- 2. What was returned to the Investigator unused, including expired or malfunctioning product.
- 3. The number and reason for unplanned replacements.

The Investigator will collect all unused test articles from the subjects at the end of the subject's participation. Subject returned unused test articles must be separated from the clinical study inventory of un-dispensed test articles and must be labeled with the subject number and date of return. Following final reconciliation of test articles by the monitor, the Investigator or monitor will return all unused test articles to JJVC.

If there is a discrepancy between the shipment documents and the contents, contact the study monitor immediately.

Site Instructions for Test Article Receipt and Test Article Accountability for additional information.

#### 7. STUDY EVALUATIONS

#### 7.1. Time and Event Schedule

Table 3: Time and Events

Event	Visit 1: Screening	Visit 1: Treatment 1	Visit 1: Treatment 2
	Baseline		
Time point		Day 0	
Visit Duration		3.5 hours	
Statement of Informed Consent	X		7
Demographics	X		
Inclusion/Exclusion Criteria	X		) 3
Medical History	X		
Concomitant Medication	X		5
Habitual Lens Information	X		
Subject Reported Ocular Symptoms		X	X
Entrance Visual Acuity	X		
Subjective Sphero-Cylindrical Refraction	X		
Subjective Best Sphere Refraction	X		) )
Entrance Slit Lamp Exam	X		
Lens Assignment	2	X	X
Lens Insertion	2	X	X
Lens Settling		X	X
Over Refraction	3	X	X
logMAR Visual performance (distance)		X	X
Cosmetic Lens Fit (without slit-lamp)	6	X	X
Hula Hoop Evaluation (without slit-lamp)		X	X
Mechanical Lens Fit Assessment		X	X
Exit Slit Lamp Exam			X
Exit Snellen Distance VA			X
Study Completion/ Adverse Event Review			X
Final Exam Form and Investigator Signature			X

### 7.2. Detailed Study Procedures

#### VISIT 1

The subject must attend the visit wearing their habitual spectacles (where applicable).

	Visit 1: Screening				
Step	Procedure	Details			
1.1	Statement of Informed Consent	Each subject must read, understand, and sign the Statement of Informed Consent before being enrolled into the study. The Principal Investigator or his/her designee conducting the informed consent discussion must also sign the consent form.  Note: The subject must be provided a signed copy of this document.			
1.2	Demographics	Record the subject's year of birth, gender, race and ethnicity.			
1.3	Medical History and Concomitant Medications	Questions regarding the subjects' medical history and concomitant medications.			
1.4	Habitual Lenses	Questions regarding the subject's habitual lens type, parameters, wear schedule and duration.			
1.5	Wear time and comfortable wear time with Habitual lenses	Record the subject's typical wear time and comfortable wear time per day with their habitual contact lenses.			
1.6	Eligibility after Screening	All responses to Screening Inclusion Criteria questions must be answered "yes" and all responses to Exclusion Criteria must be answered "no" for the subject to be considered eligible.  If subject is deemed to be ineligible after screening, proceed to Final Evaluation and complete Subject Disposition. Visual Acuity, Refraction and Biomicroscopy forms are not			

	Visit 1: Baseline		
Step Procedure Details			
1.7	Entrance Visual Acuity	Record the distance Snellen visual acuity (OD, OS, and OU) to the nearest letter with their habitual spectacles (where applicable).	

		Subjects must read the smallest line until at	
		least 50% of the letters are read incorrectly.	
1.8	Subjective Sphero- cylindrical Refraction	Complete subjective spherocylindrical refraction and record the resultant distance visual acuity (OD, OS and OU) to the nearest letter.	
1.9	Subjective Best Sphere Refraction	Perform subjective best sphere refraction with a phoropter (adopt the maximum plus to maximum visual acuity (MPMVA) approach and use the duo-chrome test for binocular balancing) and record the best corrected distance visual acuity (OD, OS, OU) to the nearest letter.  Note: The endpoint criterion for the duo-chrome test is the lens power at which the red and green sides of the chart appear to be equally distinct. However, if the subject's response changes from "red" to "green" with only a 0.25D change in power and no report that the two sides appear to be equally sharp, the refraction endpoint should be the lens power that leave the red chart sharper.  Note 2: The subject's optimal vertexed spherical equivalent distance correction must be between -1.00D and -6.00D.	
1.10	Slit Lamp Findings	FDA Slit Lamp Classification Scale will be used to grade the findings and determine eligibility.  If any of these slit lamp findings are Grade 3 or higher, the subject may not continue at this time, but may return up to one additional time to determine eligibility. If discontinued a final examination must be completed.  If the clearance of the fluorescein needs to be expedited, preservative-free rewetting drops or saline may be instilled.	
1.11	Eligibility after Baseline	All responses to Inclusion Criteria questions must be answered "yes" and all responses to Exclusion Criteria questions must be answered "no" for the subject to be considered eligible.	

	Visit 1: Treatment 1 Lens Fitting			
Step	Procedure	Details		
1.12	Lens Selection	Assign the study lens based on the randomization scheme. Select the contact lens power based on subjective best sphere refraction.		
1.13	Lens Insertion	The Investigator or the subject inserts the study lenses. Record the time of lens insertion.  Check for lens damage under the slit lamp before proceeding with lens settling.  Replace damaged lenses if applicable.  Note: Designated site staff should observe the insertion process. If it appears that the subject attempts to insert a lens that is "inside-out", they should interfere to avoid incorrect insertion.		
		Note 2: If the lens moves excessively on the eye after insertion, ask the subject to remove the lens, confirm lens is not inverted (correct if it is is) and reinsert.		
1.14	Lens Settling	Allow the study lenses to settle for a minimum of 5 minutes.		
1.15	Subjective Best Sphere Over Refraction	Perform subjective best sphere refraction over the study lenses with a phoropter (adopt the maximum plus to maximum visual acuity (MPMVA) approach and use the duo-chrome test for binocular balancing) and record the best corrected distance visual acuity to the nearest letter (OD, OS, OU).		
1.16	Lens Power Modification (if applicable)	Adjust the lens power if the subject's best sphere over-refraction is not plano. For each power modification, repeat steps (1.13 to 1.16). Only two power modifications per eye are allowed.		
1.17	Subject Reported Ocular Symptoms	Subjects will respond to a verbal open-ended symptoms questionnaire.		
1.18	Distance ETDRS LogMAR Visual Acuity-	Per please confirm room illuminance and chart luminance acceptable ranges for both high/low contrast visual acuity testing.		

		1. Under high illumination and high chart	
		luminance, record the distance (4 meter) ETDRS high contrast visual acuity OD (HC1), OS (HC2) and OU (HC3).	
		2. Under high illumination and high chart luminance, record the distance (4 meter) ETDRS low contrast visual acuity OD (LC1), OS (LC2), and OU (LC3).	
		3. With the goggles on, under high illumination and chart luminance, record the distance (4 meter) ETDRS high contrast visual acuity OD (HC1), OS (HC2) and OU (HC3). Allow subject to adjust to dim condition for 3 minutes	
		Letter-by-letter results will be recorded into the electronic data capture form, which will calculate the visual performance score for each chart read.	
1.19	Cosmetic Lens Fit Assessment (without slit-lamp)	The Cosmetic Lens Assessment will be assessed by the investigator (without slit-lamp) in primary gaze and extreme gaze (right, left, and upgaze) at a normal conversation distance (approximately three (3) feet away from the subject).	Appendix E
1.20	Hula Hoop Assessment (without slit-lamp) *if unacceptable cosmetic lens fit in any gaze*	If there is an unacceptable cosmetic fit in any gaze, the Hula Hoop Assessment will be assessed by the investigator (without slit-lamp) in primary gaze and extreme gaze (right, left, and upgaze) at a normal conversation distance (approximately three (3) feet away from the subject).	Appendix E
1.21	Subjective Lens Fit Assessment	Evaluate overall lens fit acceptance (acceptable or unacceptable) based on centration, movement and other fitting characteristics.	
		An unacceptable fit is deemed by one of the following criteria:  • limbal exposure at primary gaze or with extreme eye movement;  • edge lift;  • excessive movement in primary and up gaze; or	

		insufficient movement in all three of the following conditions: primary gaze, up gaze, and Josephson push up.  If the fit is unacceptable, the subject can continue with the study.
1.22	Remove lenses	Have subject remove lenses. Worn lenses can be discarded.
1.23	Washout	There will be a 5-minute washout between lenses

	Visit 1: Treatment 2 Lens Fitting			
Step	Procedure	Details		
1.24	Lens Selection	Assign the study lens based on the randomization scheme. Select the contact lens power based on subjective best sphere refraction.		
1.25	Lens Insertion	The Investigator or the subject inserts the study lenses. Record the time of lens insertion.  Check for lens damage under the slit lamp before proceeding with lens settling.  Replace damaged lenses if applicable.  Note: Designated site staff should observe the insertion process. If it appears that the subject attempts to insert a lens that is "inside-out", they should interfere to avoid incorrect insertion.  Note 2: If the lens moves excessively on the		
1.26	T C (1)	eye after insertion, ask the subject to remove the lens, confirm lens is not inverted (correct if it is is) and reinsert.		
1.26	Lens Settling	Allow the study lenses to settle for a minimum of 5 minutes.		
1.27	Subjective Best Sphere Over Refraction	Perform subjective best sphere refraction over the study lenses with a phoropter (adopt the maximum plus to maximum visual acuity (MPMVA) approach and use the duo-chrome test for binocular balancing) and record the best corrected distance visual acuity to the nearest letter (OD, OS, OU).		

53			
1.28	Lens Power Modification (if applicable)	Adjust the lens power if the subject's best sphere over-refraction is not plano. For each power modification, repeat steps (1.25 to 1.28). Only two power modifications per eye are allowed.	
1.29	Subject Reported Ocular Symptoms	Subjects will respond to a verbal open-ended symptoms questionnaire.	
1.30	Distance ETDRS logMAR Visual Acuity-	Per please confirm room illuminance and chart luminance acceptable ranges for both high/low contrast visual acuity testing.  4. Under high illumination and high chart luminance, record the distance (4 meter)	
		ETDRS high contrast visual acuity OD (HC1), OS (HC2) and OU (HC3).	
		5. Under high illumination and high chart luminance, record the distance (4 meter) ETDRS low contrast visual acuity OD (LC1), OS (LC2), and OU (LC3).	
		6. With the goggles on, under high illumination and chart luminance, record the distance (4 meter) ETDRS high contrast visual acuity OD (HC1), OS (HC2) and OU (HC3). Allow subject to adjust to dim condition for 3 minutes	
		Letter-by-letter results will be recorded into the electronic data capture form, which will calculate the visual performance score for each chart read.	
1.31	Cosmetic Lens Fit Assessment (without slit-lamp)	The Cosmetic Lens Assessment will be assessed by the investigator (without slit-lamp) in primary gaze and extreme gaze (right, left, and upgaze) at a normal conversation distance (approximately three (3) feet away from the subject).	Appendix E
1.32	Hula Hoop Assessment (without slit-lamp)	If there is an unacceptable cosmetic fit in any gaze, the Hula Hoop Assessment will be assessed by the investigator (without slit-lamp) in primary gaze and extreme gaze	Appendix E

	*if unacceptable cosmetic lens fit in any gaze*	(right, left, and upgaze) at a normal conversation distance (approximately three (3) feet away from the subject).	
1.33	Subjective Lens Fit Assessment	Evaluate overall lens fit acceptance (acceptable or unacceptable) based on centration, movement and other fitting characteristics.  An unacceptable fit is deemed by one of the following criteria:  Imbal exposure at primary gaze or with extreme eye movement;  edge lift;  excessive movement in primary and up gaze; or  insufficient movement in all three of the following conditions: primary gaze, up gaze, and Josephson push up. If the fit is unacceptable, the subject can continue with the study.	
1.34	Remove lenses	Have subject remove lenses. Worn lenses can be discarded.	

#### FINAL EVALUATION

The final evaluation will ordinarily take place immediately following the last scheduled follow-up visit per the study protocol. It may also take place at any point the subject discontinues the study or is terminated from the study.

Final Evaluation			
Step	Procedure	Details	
F.1	Final Exam Form	Indicate if the subject completed the study successfully. If subject discontinued from the study, indicate the reason.	

Final Evaluation					
Step	Procedure	Details			
F.2	Exit Slit Lamp Biomicroscopy	FDA Slit Lamp Classification Scale will be used to grade the findings. If no slit lamp finding is noted on the EDC form it is considered as a zero "0" Grade for all observations listed.  After the slit lamp examination, at the discretion of the Investigator, rinse the subject's eyes thoroughly with preservative-free saline.			
F.3	Exit Visual Acuity	Record the distance Snellen visual acuity (OD, OS, and OU) to the nearest letter with their habitual spectacles (where applicable). Subjects must read the smallest line until at least 50% of the letters are read incorrectly.			

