#### 7.3. Unscheduled Visits

If, during the investigation, a subject requires an unscheduled visit to the clinical site, the following information will be collected as appropriate:

- Chief complaint prompting the visit. If the reason is an adverse event, the applicable eCRF for the adverse event must be completed and subject record completed as appropriate.
- Date and time of the visit and all procedures completed at the unscheduled visit.
- Review of adverse event and concomitant medications.
- Slit lamp findings (using the Slit Lamp Classification Scale).

If the Investigator withdraws a subject from the study, the final study visit case report forms must be completed indicating the reason(s) why the subject was withdrawn. The subject record must be completed documenting the date and primary reason for withdrawal and the study CRA notified.

Any ocular and non-ocular Adverse Events that are ongoing at the time of the study visit will be followed by the Investigator, within licensure, until they have resolved, returned to pre-treatment status, stabilized, or been satisfactorily explained. If further treatment i.e., beyond licensure is required, the subject will be referred to the appropriate health care provider.

The following information will be collected during an unscheduled visit as appropriate.

Unscheduled Visit					
Step	Procedure	Details			
U.1	Chief Complaints	Record the subject's chief complaints for reasons for the unscheduled visit.			

Unscheduled Visit				
Step	Procedure	Details		
U.2	Adverse Events and Concomitant Medications Review	Review any changes to the subject's medical history or concomitant medications from the previous study visit. Record any changes, and any adverse events.	-	
U.3	Entrance VA	Record the entrance distance visual acuity (OD, OS and OU) to the nearest letter.		
U.4	Subjective Sphero- cylindrical Refraction	Perform bare-eye subjective spherocylindrical refraction with a phoropter (adopt the maximum plus to maximum visual acuity (MPMVA) approach and use the duo-chrome test for binocular balancing) and record the best corrected distance visual acuity to the nearest letter (OD, OS, and OU).		
U.5	Slit Lamp Biomicroscopy	FDA Slit Lamp Classification Scale will be used to grade the findings. If the clearance of the fluorescein needs to be expedited, preservative-free rewetting drops may be instilled.		

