#### 8.2. Withdrawal/Discontinuation from the Study

A subject will be withdrawn from the study for any of the following reasons:

- · Subject death during the study period
- Subject withdrawal of consent and/or assent
- Subject not compliant to protocol

- Subject lost to follow-up
- Subject no longer meets eligibility criteria (eg the subject becomes pregnant)
- Subject develops significant or serious adverse events causing discontinuation of study lens wear
- Subjects who have experienced a Corneal Infiltrative Event (CIE)
- Investigator's clinical judgment regarding the subject safety reasons (that it is in the best interest of the subject to stop treatment)

For discontinued subjects, the Investigator will:

- Complete the current visit (scheduled or unscheduled)
- Complete the Final Evaluation, indicating the reason that the subject was discontinued from the study
- Record the spherocylindrical refraction with best corrected distance visual acuity, as appropriate
- Collect used test article(s) (worn or brought to the visit) from the subject and discard them, unless otherwise stated in Section 7.2
- Collect all unused test article(s) from the subject

An additional subject may be enrolled if a subject discontinues from the study prematurely.

In cases where a subject is lost to follow-up, every possible effort must be made to contact the subject and determine the reason for discontinuation/withdrawal. The measures taken to follow up must be documented including two written attempts and a certified letter (or equivalent) as the final attempt.

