#### 13. ADVERSE EVENTS

#### 13.1. Definitions and Classifications

**Adverse Event (AE)** – An AE is "any untoward medical occurrence, unintended disease or injury, or untoward clinical signs (including abnormal laboratory findings) in subjects, users or other persons, whether or not related to the investigational medical device. This definition includes events related to the investigational medical device or the comparator, and to the procedures involved. For users or other persons, this definition is restricted to events related to investigational medical devices

An AE includes any condition (including a pre-existing condition) that:

- 1. Was not present prior to the study, but appeared or reappeared following initiation of the study.
- 2. Was present prior to the study, but worsened during the study. This would include any condition resulting from concomitant illnesses, reactions to concomitant medications, or progression of disease states.
- 3. Pregnancy must be documented as an adverse event and must be reported to the clinical monitor and to the Sponsor immediately upon learning of the event.

**Serious Adverse Event (SAE)** – An SAE is any adverse event that led to any of the following:

- Death
- Serious deterioration in the health of the subject that resulted in any of the following:
- Life-threatening illness or injury
- Permanent or persistent impairment of a body structure or a body function
- Hospitalization or prolongation of patient hospitalization
- Medical or surgical intervention to prevent life-threatening illness or injury or permanent impairment to a body structure or a body function.
- Chronic disease
- Fetal distress, fetal death or a congenital physical or mental impairment of birth defect.

Diagnoses and conditions that are considered Ocular Serious Adverse Events include, but not limited to:

- Microbial Keratitis (MK)
- Iritis (including cells in the anterior chamber)
- Permanent decrease in best spectacle corrected visual acuity equivalent to 2 acuity lines or greater

- Central Corneal Opacity
- Central Corneal Neovascularization
- Uveitis
- Endophthalmitis
- Hypopyon
- Hyphemia
- Penetration of Bowman's Membrane
- Persistent Epithelial Defect
- Limbal cell Damage leading to Conjunctivalization

**Significant Adverse Events** – are defined as events that are symptomatic and warrant discontinuation (temporary or permanent) of the contact lens wear

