Diagnoses and conditions that are considered Ocular Significant Adverse Events include, but not limited to the following:

- Contact Lens Induced Peripheral Ulcer (CLPU)
- Significant Infiltrative Events (SIE)
- Superior Epithelial Arcuate Lesions (SEALs)
- Any Temporary Loss of > 2 Lines of BSCVA
- Other grade 3 or higher corneal findings, such as abrasions or edema
- Non-contact lens related corneal events e.g. Epidemic Keratoconjunctivitis (EKC)
- Asymptomatic Corneal Scar
- Any corneal event which necessitates temporary lens discontinuation > 2 weeks

**Non-Significant Adverse Events** – are defined as those events that are usually asymptomatic and usually do not warrant discontinuation of contact lens wear but may cause a reduction in wear time. However, the Investigator may choose to prescribe treatment as a precautionary measure.

Diagnoses and conditions that are considered Ocular Non-Significant Adverse Events include, but not limited to the following:

- Non-significant Infiltrative Event (NSIE)
- Contact Lens Papillary Conjunctivitis (CLPC)
- Superficial Punctate Keratitis (SPK)
- Conjunctivitis: Bacterial, Viral, Allergic
- Blepharitis
- Meibomianitis
- Contact Dermatitis
- Localized Allergic Reactions
- Any corneal event not explicitly defined as serious or significant adverse event, which necessitates temporary lens discontinuation < 2 weeks

**Adverse Device Effect (ADE)** – An ADE is an "adverse event related to the use of an investigational medical device.

**NOTE 1:** to entry: This definition includes adverse events resulting from insufficient or inadequate instructions for use, deployment, implantation, installation, or operation, or any malfunction of the investigational medical device.

**NOTE 2** to entry: This definition includes any event resulting from use error or from intentional misuse of the investigational medical device."

Unanticipated Adverse Device Effect (UADE) – Any serious adverse effect on health or safety or any life-threatening problem or death caused by, or associated with, the test article, if that effect, problem, or death was not previously identified in nature, severity, or degree of incidence in the investigational plan, Investigator's Brochure or protocol, or any other unanticipated serious problem associated with the test article that relates to the rights, safety and welfare of subjects.

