## 13.3. Documentation and Follow-Up of Adverse Events

The recording and documenting of adverse events (ocular and non-ocular) begin when the subjects are exposed to the test article, study treatment or study procedure. Adverse events reported before the use of test article, start of study treatment, or study procedures will be recorded as medical history. However, if the condition deteriorates at any time during the study it will be recorded and reported as an AE. Untoward medical events reported after the subject's exit from the study will be recorded as adverse events at the discretion of the Investigator.

Upon finding an adverse event, the Principal Investigator will document the condition in the subject record and in the eCRFs. He/she will complete the Adverse Event /eCRF.

Complete descriptions of all adverse events must be available in the subject record. All Adverse Events including local and systemic reactions not meeting the criteria for "serious adverse events" shall be captured on the appropriate case report form or electronic data system. All adverse events occurring while the subject is enrolled in the study must be documented appropriately regardless of relationship.

It is the Investigator's responsibility to maintain documentation of each reported adverse event. All adverse events will be followed in accordance with applicable licensing requirements. Such documentation will include the following:

- Adverse event (diagnosis not symptom).
- Drawings or photographs (where appropriate) that detail the finding (e.g., size, location, and depth, etc.).
- Date the clinical site was notified.
- Date and time of onset.
- Date and time of resolution.
- Adverse event classification, severity, and relationship to test articles, as applicable.
- Treatment regimen instituted, including concomitant medications prescribed, in accordance with applicable licensing requirements.

- Any referral to another health care provider if needed.
- Outcome, ocular damage (if any).
- Likely etiology.
- Best corrected visual acuity at the discovery of the event and upon conclusion of the event, if related to the visual system.

In addition, if an infiltrate(s) is present, he/she will complete the Corneal Infiltrate Assessment eCRF. Where necessary, a culture of the corneal lesion will be collected to determine if the infection is microbial in nature. If cultures are collected, the date of culture collection and laboratory utilized will be recorded.

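### For completers with no recognised event, the visual-loss criteria in Section 13.1 (defined on best spectacle-corrected acuity) cannot be evaluated from the scheduled exit data

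*Combined protocol and SAP*

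**What the plan says.** Section 13.1 has two criteria for loss of vision, both on best spectacle-corrected visual acuity (BSCVA). The serious list includes "Permanent decrease in best spectacle corrected visual acuity equivalent to 2 acuity lines or greater". The significant list includes "Any Temporary Loss of > 2 Lines of BSCVA".

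The baseline for either comparison comes from step 1.8 in Section 7.2: "Complete subjective spherocylindrical refraction and record the resultant distance visual acuity (OD, OS and OU) to the nearest letter".

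At exit, step F.3 reads: "Record the distance Snellen visual acuity (OD, OS, and OU) to the nearest letter with their habitual spectacles (where applicable"). The Table 3 entry for this is "Exit Snellen Distance VA". Table 3 marks spherocylindrical refraction in the screening/baseline column only. Entrance acuity at step 1.7 carries the same instruction as F.3.

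Best-corrected acuity after lens exposure is provided for in three other situations:

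- Discontinued subjects (Section 8.2): "Record the spherocylindrical refraction with best corrected distance visual acuity, as appropriate".
- Unscheduled visits (step U.4, collected as appropriate): "Perform bare-eye subjective spherocylindrical refraction with a phoropter", with the resulting acuity recorded.
- Documentation of an adverse event (Section 13.3): "Best corrected visual acuity at the discovery of the event and upon conclusion of the event, if related to the visual system".

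The synopsis names entrance and exit acuity among the safety parameters.

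**The concern.** The safety criterion and the scheduled safety measurement use different corrections. A subject who completes uneventfully has one BSCVA on record, from baseline, and none after wearing the lenses. Whether that subject lost two lines on the scale used by Section 13.1 cannot be read from the scheduled data.

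This matters most where the habitual correction is poor or absent. All subjects are contact lens wearers with -1.00 D to -6.00 D of myopia, and the protocol expects spectacles only if the subject has them. The visible text does not say what correction a subject without spectacles should use. If such a subject is read unaided, defocus limits acuity at both entrance and exit, and a modest loss from the cornea or media can be hidden beneath it. Outdated spectacles do the same to a lesser degree.

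Reporting is also affected. Section 1.5 summarises earlier studies as showing no loss of best-corrected acuity. For uneventful completers, this study's scheduled exit data could not directly support the same statement.

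**Working it through.** The plan states no figure on this point, so the check compares the acuity measurements one by one with what Section 13.1 needs: a spectacle-plane, best-corrected value after wear, to set against step 1.8.

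| Measurement | Correction | Who and when | Post-wear BSCVA? |
|---|---|---|---|
| Step 1.7 | Habitual spectacles, if any | All, before wear | No |
| Step 1.8 | Full spherocylindrical refraction | All, before wear | No; this is the baseline |
| Step 1.9 | Best sphere | All, before wear | No |
| Steps 1.15, 1.18 | Through study lens, period 1 | All, during wear | No |
| Steps 1.27, 1.30 | Through study lens, period 2 | All, during wear | No |
| Step F.3 | Habitual spectacles, if any | All, after final removal | No |
| Section 8.2 | Refraction, as appropriate | Discontinued subjects only | Yes, if done |
| Step U.4 | Bare-eye refraction, as appropriate | Unscheduled visits only | Yes, if done |
| Section 13.3 | Best corrected | Recognised visual events only | Yes |

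For a completer with no recognised event and no unscheduled visit, the count of BSCVA values is one before wear and none after. F.3 is the only acuity reading after the final lens removal.

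The route from F.3 to a best-corrected value is Section 13.3, which starts when an event is discovered. The visible text states no entrance-to-exit change that counts as discovery.

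**How many subjects.** The documents do not give the share without usable spectacles. As an assumption only, at 10% to 30%: 0.10 × 34 = 3.4 and 0.30 × 34 = 10.2, or about 3 to 10 of the 34 planned completers.

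**How large a loss could be hidden.** Assume 0.10 logMAR per line and a Snellen chart whose largest steps are 20/200 and 20/400; the chart is not specified in the visible text. The step is log10(400/20) − log10(200/20) = 1.301 − 1.000 = 0.301 logMAR. Two lines are 0.20 logMAR. A loss between 0.20 and 0.30 logMAR exceeds two lines, so it passes the size threshold of the significant criterion, yet it is smaller than one chart step. A loss of exactly 0.20 does not meet that criterion, which requires more than two lines.

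**What F.3 cannot settle in any form.** The serious criterion requires a permanent decrease. Table 3 puts the whole study in one visit of 3.5 hours, so no exit reading, however corrected, can establish permanence.

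**The case against.** The strongest reply is that the criteria classify events, and the protocol collects the right measure for events. Section 13.3 requires best-corrected acuity at discovery and conclusion, U.4 provides a refraction, and step 1.8 supplies the baseline. This stands. A reader might infer from F.3 that the Section 13.1 criteria cannot be applied at all; the documents do not support that.

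A reader might also infer that F.3 is the sole check on vision and that a loss would be missed. That is also too strong:

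- Entrance and exit readings use the same instruction, so they are like for like, and they serve their purpose in subjects with adequate spectacles.
- In period 2, steps 1.27 and 1.30 record acuity through the study lens in each eye, whether or not the subject owns spectacles. A clear loss carried over from period 1, or arising before step 1.30, should show there.
- Symptoms are asked about in each period, and a slit lamp examination and an adverse event review take place at exit.

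These give partial cover and do not close the gap. The symptom questions at 1.17 and 1.29 come before lens removal. The slit lamp shows signs and does not measure acuity. Section 13.1 describes significant events as symptomatic but lists an asymptomatic corneal scar among them, so absence of symptoms does not rule such an event out.

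Four further points stand. Refraction of discontinued subjects is itself only as appropriate, so their contrast with completers is softer than it first appears. Lens wear is short, about 90 minutes per lens (Section 1.2), and Section 1.5 reports no earlier loss of best-corrected acuity, so events should be rare. The acuity procedures in Appendix D are not legible in the available text and may contain an instruction for subjects without spectacles or a recheck rule; Table 3 would still schedule no exit refraction. Finally, reading through the step 1.8 correction is not a fresh best-corrected acuity, so it can serve only as a screen.

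**Conclusion.** The point holds in a limited form. For completers with no recognised event, the scheduled exit data cannot show whether a Section 13.1 visual-loss threshold was reached, and detection rests on an unstated trigger from an acuity reading whose correction is undefined for some subjects. The practical weight falls on myopes with no spectacles or outdated ones.

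The table of measurements rests on the documents alone. The count of 3 to 10 subjects and the chart-step illustration rest on the assumptions stated with them and should not be cited as findings about this trial. The conclusion about a missing trigger is confined to the visible text.

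This is a cheap improvement to a named safety measurement. It does not touch the primary endpoint, the sample size or the error rate.

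**What to change.** In F.3, read exit distance acuity (each eye and both together) through the spherocylindrical correction recorded at step 1.8, and compare it with the step 1.8 acuity. Describe this as a screen. State what change leads to the best-corrected measurement that Section 13.3 already requires; the choice of that change is for the sponsor. The habitual-spectacle reading can stay as an optional extra to preserve the comparison with step 1.7.

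Then reconcile Table 3, step F.3, Section 8.2, the two criteria in Section 13.1 and Section 13.3, so that the correction used at exit and the route to classification agree. If Appendix D already gives a rule for subjects without spectacles or for a recheck, cite it in F.3.

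The cost is an estimated two minutes per subject: 34 × 2 = 68 minutes over the planned completers, or 40 × 2 = 80 minutes if all enrolled subjects reach exit. It also needs small wording changes. The phoropter is already in use at steps 1.9, 1.15 and 1.27, and no new refraction is needed for the screen. The downside is that a transient refractive shift may read as a loss and prompt a repeat refraction.
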